ID: IB2019-METABONE

Patterns of Care and Outcomes in Patients With Metastatic Bone Tumors (METABONE)

NCT03963531

Jan 5, 2007

INCLUSION

- Patients age > 12 year old at initial diagnosis
- Histology of Ewing's sarcoma type, osteosarcoma, chondrosarcoma
- Diagnostic of primary event between 2008 and 2018
- Diagnostic of unresectable locoregional disease where palliative treatment is indicated, or metastatic disease
- Treatment and monitoring made in one of the GSF-GETO centers, with follow up data on treatment received available.

OBJECTIFS

I. OBJECTIVES AND ENDPOINTS

The primary objective of the METABONE study is to give a retrospective descriptive analysis of clinico-biological profiles, patterns of care and modalities of treatment of patients with unresectable locally advanced and/or metastatic malignant bone tumors in a real-life national setting.

The primary endpoint is description of initial and local/metastatic relapse events management of adult patients with the diagnosis of Ewing's sarcoma, osteosarcoma, chondrosarcoma, made in one of the centers of the RESOS network between 2008 and 2018, in terms of therapeutic strategies including chemotherapy, surgery, radiotherapy, interventional radiology.

Secondary endpoints

- Description of systemic treatments received in the palliative setting in terms of **PFS** (progression free survival) and **TNT** (Time to next treatment)
- **Overall survival** from unresectable locally advanced and/or metastatic stage
- Identification of **factors associated with PFS and TNT** for molecules used in the unresectable locally advanced and metastatic setting
- Identification of **prognostic factors for overall survival** (OS) in the unresectable locally advanced and/ metastatic setting

II. METHODS

PATIENTS

We estimate the population size in the database of about 2800 patient cases.

We seek to include 800 patients to be screened in the present study.

We aim to get about 400 to 500 informative patients with unresectable locally advanced or metastatic disease.

VARIABLES

Variables collected will be those of the **CONTICABONE DICTIONNARY**

Descriptive data

Centers, number of patients per center

Initial patients characteristics at diagnostic: Age at diagnosis, gender, PS at diagnosis, previous history of specific disease (Li Fraumeni, Multiple Exostosis)

Tumor characteristics at diagnostic : location, side, size, multifocality, LR spread and type, stage N M, histology, grade, previous radiation area,

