Initial treatment: surgery, type of surgery, margins, tumor spillage, residual cellularity, neo/adjuvant systemic treatment indication (start and stop date, type), radiation therapy, other treatment (cryotherapy, radiofrequency, embolisation), clinical trial inclusion

Metastatic relapse/event characteristics: PS, location of first metastasis, number of sites

Treatment of metastatic event: systemic treatment (PS molecule used, start and stop date, best RECIST response, date of progression, clinical trial), locoregional treatment (surgery, radiotherapy, cryotherapy, radiofrequency, embolisation), clinical trial.

Dates: Birth, initial diagnostic, surgery of primary, local relapse, metastatic relapse, start of each chemo line, date of progression for each chemo line, last contact, death

Samples: Molecular cytogenetics : method (RT PCR, FISH), transcript (FOR EWING SARCOMA ONLY)

Survival data

Median follow up

Progression free survival (PFS): PFS defined as the time from the systemic treatment onset to progression or death due to any cause, whichever comes first. When neither death nor progression is observed, PFS is censored at the date of last patient contact.

Time to next treatment (TNT): TNT defined as the time from the systemic treatment onset to the next treatment or death due to any cause, whichever comes first. When neither death nor new systemic therapy is observed, TNT is censored at the date of last patient contact.

Overall survival (OS): OS is defined as the interval between the diagnosis of first tumor event and the time of death. OS in the unresectable locally advanced setting is defined as the interval between the diagnosis of unresectable locally advanced setting (at diagnosis or relapse) and the time of death. OS in the metastatic setting is defined as the interval between the diagnosis of metastatic disease (at diagnosis or relapse) and the time of death. When death is not observed, OS is censored at the date of last patient contact.

STATISTICS

Statistical analysis of the baseline demographics and clinical outcomes will be based on all data available up to the cut-off date of August 31, 2021.

Descriptive statistics will be used to show the distribution of variables in the population.

The variables included in the univariate and multivariate analyses are the descriptive data including:

- type of chemotherapy used (poly vs mono, class of chemo: TKI, Ifosfamide, other)
- locoregional treatment of metastasis,

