- inclusion in a clinical trial in first line,
- at least one inclusion in a clinical trial during metastatic stage,
- use of off-label drug at least once during metastatic stage

Multivariate logistic regression models will be used to identify biological and clinical factors associated with the type of treatment received after 1st line: in second, third, 4th line, and with the probability of survival 5 years after the diagnosis of metastases.

Follow-up times will be described as median values based on the inverse Kaplan–Meier estimator.

Prognostic factors of TNT for each line (1st, second, Third) and OS will be identified using Cox proportional hazard models.

The correlation between TNT and OS will be evaluated at each of the four first-lines of metastatic chemotherapy by a Spearman rank correlation coefficient and expressed as a value between 0 (no association) and 1 (perfect association). We will use a reviewed copula-based approach that introduces an iterative multiple imputation method for the estimation of the correlation coefficient. The data will be analyzed using the SAS v9.3 and R v3.3 software packages.

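### PFS has no rule for a new line started without a recorded progression, so time on later lines can be credited to the earlier drug

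*Combined protocol and SAP*

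**What the plan says.** Under II. Methods, Variables, Survival data, the start and events are given as: "PFS defined as the time from the systemic treatment onset to progression or death due to any cause, whichever comes first". The only censoring rule is: "When neither death nor progression is observed, PFS is censored at the date of last patient contact". A change of systemic line is neither an event nor a reason for censoring. The text also does not say whether a progression recorded under a later line ends the PFS of the earlier one.

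The neighbouring definition does use the line change: "TNT defined as the time from the systemic treatment onset to the next treatment or death due to any cause, whichever comes first".

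The Dates list in the same section includes "start of each chemo line, date of progression for each chemo line, last contact, death". A line change without a preceding progression date can therefore be found in the data.

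Under I. Objectives and Endpoints, PFS is a secondary endpoint, introduced as "Description of systemic treatments received in the palliative setting in terms of" PFS and TNT. Factors associated with both are sought for "molecules used in the unresectable locally advanced and metastatic setting". The Statistics section names models for TNT and OS only: "Prognostic factors of TNT for each line (1st, second, Third) and OS will be identified using Cox proportional hazard models".

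**The concern.** PFS is measured from the start of a systemic treatment and read as a property of the molecule given. The data are retrospective and come from many centres, so the end of PFS depends on whether a progression date was entered. If a line ends with a switch and no date, the written rule keeps the patient progression-free on the earlier line while later drugs are being given. A missing date becomes additional PFS for the earlier drug.

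Per-line and per-drug PFS would then be too long wherever a switch hides a real progression. If completeness of recording differs by drug class, period or centre, a contrast between classes (the Statistics section lists poly versus mono and TKI, ifosfamide, other) would partly reflect charting. For the same patient and line, TNT would stop at the switch while PFS ran on, and nothing in the plan would tell the reader how often this happens.

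**Working it through.** The plan states no PFS figure and no share of line changes without a recorded progression, so there is nothing to reproduce. The calculations below show direction and order of size. All their inputs are assumptions.

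**1. Closed-form check, PFS running to death or last contact**

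Assume exponential times, a true median PFS of 4 months, a median of 10 months from progression to death, and a share q of progressions unrecorded at random.

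- Recorded patients: S(t) = 2^(−t/4).
- Unrecorded patients are followed to death, the sum of the two times: S(t) = (5/3)·2^(−t/10) − (2/3)·2^(−t/4). Here 5/3 = 0.25/(0.25 − 0.10) and 2/3 = 0.10/(0.25 − 0.10).
- Mixture: F(t) = (1 − 5q/3)·2^(−t/4) + (5q/3)·2^(−t/10).

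For q = 20%, F(t) = (2/3)·2^(−t/4) + (1/3)·2^(−t/10). At t = 5.25 this is 0.268 + 0.232 = 0.500, so the median is about 5.3 months. At 12 months it is (2/3)(0.125) + (1/3)(0.435) = 0.228, against a true 12.5%.

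The same formula gives medians of 4.6 and 6.1 months at q = 10% and 30%. Twelve-month PFS is (5/6)(0.125) + (1/6)(0.435) = 17.7% at 10% and (1/2)(0.125) + (1/2)(0.435) = 28.0% at 30%.

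**2. Simulation, comparing the possible rules**

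There are 200,000 patients with the same two medians. Second-line median PFS is 3 months, the next line starts 0.5 month after progression, and follow-up is uniform over 24 to 96 months. Only patients who reach a next line can have an unrecorded first progression. Second-line progressions are taken as recorded. Kaplan–Meier medians in months (true value 4.0):

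| Rule | q = 0 | 10% | 20% | 30% |
|---|---|---|---|---|
| As written, to death or last contact | 4.0 | 4.5 | 5.2 | 6.1 |
| As written, later-line progression ends PFS | 4.0 | 4.4 | 4.7 | 5.1 |
| Censor at new line | 4.0 | 4.5 | 5.0 | 5.8 |
| New line counted as event | 4.0 | 4.0 | 4.1 | 4.2 |

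The first row agrees with step 1 to within about 0.1 month. The small gap arises because patients who die before a new line keep their recorded progression.

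**3. Why censoring at the new line does little**

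Under the step 1 model, with the switch at progression, censoring removes a share q of events exactly when they occur. The observed hazard is (1 − q) times the true one, and the median is 4/(1 − q): 4.44, 5.00 and 5.71 months at 10%, 20% and 30%. At 20%, the excess left is (5.00 − 4)/(5.25 − 4) = 80% of the as-written excess.

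**4. Switches that are not progressions**

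Let 20% of patients also be at risk of a toxicity switch (median time 3 months) before progression.

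- With all progressions recorded and counted, the written rule gives 4.0 months (no bias) and the event version gives 3.3 (too low).
- With 20% of progressions unrecorded as well, the written rule gives 5.3 and the event version 3.4.

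**The case against.** The strongest reply is that the written rule is a legitimate definition. Following a patient to first progression or death regardless of later therapy is an accepted treatment-policy estimand. For a switch due to toxicity or a planned change, it does not overstate PFS, and step 4 confirms this when progressions are recorded. That stands. What remains is that the plan does not say it chose this estimand, and the choice fits poorly with attributing PFS to a molecule.

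Three stronger readings are tempting and are not supported:

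- **That PFS in this study is overstated.** The documents do not show how many line changes lack a progression date. The 10% to 30% range is assumed, and with complete recording there is no bias.
- **That affected patients always run on to death or last contact.** Progression is an event, the definition does not restrict it to the same line, and progression dates are collected for each line. A later-line progression may end PFS, which cuts the excess at 20% from about 1.2 to 0.7 months.
- **That the PFS and TNT definitions contradict each other.** They are different endpoints, and PFS longer than TNT is expected after a switch without progression.

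Reach is also limited. The primary objective is descriptive, PFS is secondary, and the Cox models and the correlation analysis in the Statistics section name TNT and OS. Factors for PFS are nevertheless a listed secondary endpoint, so the gap has consequences.

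**Conclusion.** The concern holds in a conditional form. The PFS definition has no rule for a new line started without a recorded progression, and as written it credits time on later lines to the earlier drug. Where such a switch hides a real progression, the bias in that line's PFS is upward.

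The size cannot be known from the documents. For an assumed true median of 4 months with 10% to 30% of progressions unrecorded, the median is about 4.5 to 6.1 months under the longer reading and 4.4 to 5.1 months if later-line progressions count. These figures rest on exponential times, a 10-month median from progression to death, and progressions missing at random. The second range also assumes a 3-month second-line median with its progressions recorded.

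This deserves a change because PFS is reported by molecule and the remedy is cheap. It does not affect the primary objective.

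**What to change.** Add to the PFS definition and the Statistics section:

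1. A statement of whether a progression recorded under a later line ends the PFS of the earlier line.
2. A table, by line and drug class, of the number of line changes without a recorded progression.
3. PFS with the start of a new systemic line counted as an event (progression, new systemic line or death, whichever is first), shown beside the as-written PFS. This differs from TNT because it still stops at a recorded progression.

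Censoring at the new line may be added as a further sensitivity analysis. It should not be the sole remedy: the censoring is informative and, in the illustration, leaves about 80% of the excess in the median.

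The dates needed are already on the collection list, so the cost is a few sentences, one table and one or two extra runs. The downside is that the event version can understate PFS where switches are for toxicity or planned. The two versions should therefore be read as bounds. They are approximate, because a delay between progression and the new line can leave the event version slightly high (4.1 against 4.0 months at 20%).

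### PFS is censored at last patient contact and no tumour-assessment date is listed, so it can be overstated by an amount the listed data cannot check

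*Combined protocol and SAP*

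**What the plan says.** The Survival data section defines the endpoint: "PFS defined as the time from the systemic treatment onset to progression or death due to any cause, whichever comes first". Its censoring rule is "When neither death nor progression is observed, PFS is censored at the date of last patient contact". TNT and OS are also censored at last contact.

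The Dates item ends with "start of each chemo line, date of progression for each chemo line, last contact, death". The item on treatment of the metastatic event adds, for each systemic treatment, "start and stop date, best RECIST response, date of progression, clinical trial". Best response is listed without a date. Neither item lists the date of a tumour assessment, and no imaging schedule, rule for missed assessments or sensitivity analysis on the censoring date is given.

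Two further statements bear on this. The Variables section says "Variables collected will be those of the" study dictionary, which is not part of the documents. The inclusion criteria require "Treatment and monitoring made in one of the GSF-GETO centers, with follow up data on treatment received available".

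PFS is a secondary endpoint ("Description of systemic treatments received in the palliative setting in terms of" PFS and TNT), and a further secondary endpoint concerns factors associated with PFS and TNT for the molecules used.

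**The concern.** Last contact suits OS and TNT because contact can reveal a death or a new treatment. It is weaker for progression, which usually has to be looked for. In a retrospective study of palliative treatment, assessment may thin out or stop after a line ends while the patient is still seen or traced. Under the plan's rule such a patient stays in the PFS risk set with little chance of having a progression recorded. If the patient later dies, the event is dated at death, not at the unrecorded progression.

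Both effects push PFS upward. At stake is the PFS description of palliative treatments. If the gap between assessment and contact differs by molecule or centre, comparisons between them are distorted too.

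**Working it through.** The plan has no figure to reproduce: it gives no PFS rate, event count or assessment interval, and its 400 to 500 informative patients are a feasibility target.

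**Mechanism.** At time t let the risk set hold n_a patients still assessed and n_u patients in contact but no longer assessed. If progression is recorded only among the n_a, the Kaplan-Meier step is d/(n_a + n_u) instead of d/n_a. The estimated progression hazard is multiplied by n_a/(n_a + n_u), which is below 1 whenever n_u > 0. With no gap, n_u = 0 and the two censoring rules agree.

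**Inputs from the plan.** The PFS event (progression or death) and the censoring date (last contact).

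**Assumed inputs.**
- Exponential time to progression, with the true median m varied.
- Median survival after progression of 8 months.
- A share q of patients whose assessment stops at a random time within 0 to 12 months.
- Contact continuing for g months after the last assessment.
- In the gap, progression goes unrecorded, but a death is an event at the death date.

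**Simulated Kaplan-Meier medians in months (200,000 patients per scenario).** In the last-assessment column, deaths in the gap are also censored at the last assessment.

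| m | q | g | Plan rule | Censored at last assessment | Excess |
|---|---|---|---|---|---|
| 4 | 20% | 0 | 3.99 | 3.99 | 0% |
| 4 | 10% | 3 | 4.07 | 4.00 | 4.07/4.00 − 1 = 2% |
| 4 | 20% | 6 | 4.16 | 4.00 | 4% |
| 4 | 30% | 12 | 4.25 | 4.00 | 6% |
| 6 | 30% | 6 | 6.56 | 6.00 | 9% |
| 12 | 30% | 12 | 13.98 | 11.98 | 17% |

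A separate run of the same kind of model, with q from 10% to 30% and g from 3 to 12 months, gave about 1% to 6% at m = 4 and 2% to 12% at m = 8. The highest single value in the tabulated run at m = 4 was 4.27, which is 7% above the nominal 4.00 but 6% above that run's own last-assessment median of 4.02. The difference between runs is simulation noise.

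In absolute terms, 6% of 4 months is 0.24 months (about 7 days) and 12% of 8 months is 0.96 months (about 29 days).

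**Why deaths matter to the size.** If deaths in the gap are left out of the model, the upper figure at m = 8 becomes 7.98 versus 9.35, or 17%. The plan counts deaths as PFS events, so 12% is the figure to use at that median.

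**Why the fix needs a rule for deaths.** If only the censoring date moves and late deaths stay events, the median is 4.09 at m = 4 (q = 30%, g = 12) and 11.74 at m = 12 (same q and g). The remaining error is small but can go either way.

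**Informative stopping.** Suppose 20% of patients stop assessment 0 to 2 months before progression, with m = 4 and g = 6. The plan's rule then overstates the median by about 29% (4 × 1.29 = 5.2 months) and censoring at last assessment by about 19% (4 × 1.19 = 4.8 months).

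**The case against.** Much of the case on the other side stands.

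- **The dictionary is not shown.** A reader might infer that no assessment date is collected. The documents support only that none is listed. The Dates item is visibly incomplete, since treatment stop dates appear elsewhere in the variable list.
- **The gap is unknown.** A reader might infer that PFS is overstated. That requires last contact to fall after the last assessment in lines with no recorded progression, and the documents give neither the length nor the frequency of such gaps. Progression is not defined as imaging-only and monitoring in a network centre is required, so contact may itself reveal clinical progression, although this is not guaranteed.
- **The size is modest beside sampling error.** With 50 events (assumed), an exponential median has a 95% interval of exp(±1.96/√50), about −24% to +32%. This stands, but the censoring error has a fixed direction and does not shrink with more patients.
- **The remedy is partial.** If assessment stops because progression is near, censoring at the last assessment removes only part of the bias, as shown above.

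A reader might also infer that trial and non-trial lines would be compared unfairly because trial patients are scanned more often. The documents do not support making that part of this point. They give no assessment schedules, the Statistics section specifies Cox models for TNT and OS but not for PFS, and the timing of detection is a separate matter that the censoring date does not cause.

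**Conclusion.** The point holds in a limited form. The PFS rule credits any time between last assessment and last contact as progression-free, and the listed variables do not allow that time to be found. The direction of error is upward. Its size cannot be derived from the documents. The ranges of 1% to 6% and 2% to 12% rest on random stopping and the other inputs above; the error is zero if there is no gap, and larger with slower-progressing disease or informative stopping.

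The primary endpoint describes management and is untouched. TNT and OS are also unaffected, provided that contact captures new treatment and death. This is a minor point on one secondary endpoint, worth making because the correction is small.

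**What to change.** 1. Check whether the dictionary already holds, for each systemic line, the date of the last tumour assessment or documented disease evaluation without progression. If not, add it.
2. Replace the PFS censoring sentence with: *If neither progression nor death is observed, PFS is censored at the last documented disease evaluation without progression, or at treatment onset if there was none.*
3. State how deaths after a long unassessed gap are counted (event at the death date, or censored at the last evaluation), and define a long gap before analysis.
4. Report the last-contact rule as a sensitivity analysis.
5. If the date cannot be retrieved, keep the present rule but add a sensitivity analysis that ends PFS follow-up, in lines with no recorded progression or death, at the treatment stop date or the next-line start, both already listed. State the limitation.
6. Keep last contact for TNT and OS.

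**Cost.** One sentence if the date is already held. Otherwise one extra date per line, which may mean returning to records across centres for the expected 400 to 500 informative patients. PFS follow-up becomes shorter and medians slightly less favourable. The change reduces the bias but does not remove it when assessment stops for reasons linked to progression.

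### Unqualified OS starts at the first tumor event in a cohort entered only at unresectable or metastatic disease, and the Cox and TNT-OS analyses do not say which OS clock they use

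*Combined protocol and SAP*

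**What the plan says.** The protocol and SAP are one document. The relevant places are these.

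- **Inclusion.** A patient must have "Diagnostic of unresectable locoregional disease where palliative treatment is indicated, or metastatic disease". The primary event is limited by "Diagnostic of primary event between 2008 and 2018".
- **Objectives and endpoints, Secondary endpoints.** OS is wanted "from unresectable locally advanced and/or metastatic stage". A further endpoint asks for prognostic factors for OS in that same advanced setting.
- **Methods, Survival data.** Three definitions stand in one paragraph. The unqualified one reads "OS is defined as the interval between the diagnosis of first tumor event and the time of death". The second reads "OS in the unresectable locally advanced setting is defined as the interval between the diagnosis of unresectable locally advanced setting (at diagnosis or relapse") to death. The third reads "OS in the metastatic setting is defined as the interval between the diagnosis of metastatic disease (at diagnosis or relapse) and the time of death". Patients not known to have died are censored at last contact. Delayed entry and landmark analysis are not mentioned.
- **Statistics.** "Prognostic factors of TNT for each line (1st, second, Third) and OS will be identified using Cox proportional hazard models". The TNT-OS correlation also names OS without an origin. The logistic model for five-year survival, by contrast, is explicitly timed from the diagnosis of metastases. The analysis uses "all data available up to the cut-off date of August 31, 2021".

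**The concern.** Entry to the cohort depends on something that happens after the unqualified OS clock has started. Patients who relapse into advanced disease carry a stretch of time, from first diagnosis to relapse, in which death was impossible by construction. Patients already advanced at diagnosis carry none. Patients who never progress are absent altogether. OS from the first event in this cohort is therefore neither the survival of bone tumor patients nor survival with advanced disease.

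The prognostic analysis is the more exposed part. The candidate covariates are the descriptive data, which include stage at diagnosis, initial surgery, margins and neo/adjuvant treatment. On the first-event clock, a factor that tracks time to relapse can look prognostic without having any effect once disease is advanced. Because the Cox sentence names no origin, the analyst could take any of three clocks, and the literal choice is the biased one.

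**Working it through.** **Plan's own figure.** There is none to reproduce. The documents give no OS median, survival rate, event count or effect size, and the 400 to 500 informative patients are a recruitment aim.

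**Step 1: match each analysis to a clock.**

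| Analysis | Origin the document gives |
|---|---|
| OS secondary endpoint | Advanced stage; matched by two setting-specific definitions |
| Prognostic-factor endpoint | Advanced setting, in words |
| Cox models for OS | None stated |
| TNT-OS correlation | None stated |
| Five-year logistic model | Diagnosis of metastases |

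The setting-specific definitions carry no rule for a patient who is first unresectable and later metastatic. The list of dates under Variables has initial diagnosis, local relapse and metastatic relapse, but no date of unresectability.

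**Step 2: mechanism.** Write total time T = L + P, where L is time from first diagnosis to the advanced event (0 if advanced at diagnosis) and P is survival after it. Nobody in the cohort can die before L. If P has the same distribution for everyone, T is still longer for relapsers.

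**Step 3: size at the median.** All inputs are assumed: a share s entering at relapse, L exponential with median r in relapsers, P exponential with median m for everyone. With rates a = ln2/m and b = ln2/r, and complete follow-up,

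S(t) = (1 - s)·exp(-a·t) + s·[b·exp(-a·t) - a·exp(-b·t)]/(b - a).

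When r = m, the bracketed ratio becomes (1 + a·t)·exp(-a·t). The median solves S(t) = 0.5.

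Example with s = 0.5, m = 12, r = 24 months. Put u = 2^(-t/24). Then exp(-b·t) = u, exp(-a·t) = u², and the relapser term is 2u - u². So S = 0.5u² + 0.5(2u - u²) = u, and u = 0.5 gives t = 24.0 months, against 12.0 from the advanced event.

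**Step 4: size of the hazard ratio.** Same inputs, simulated with the primary diagnosis uniform over 2008-2018 and censoring at the August 2021 cut-off. Patients whose relapse would fall after the cut-off are excluded. The Cox covariate is advanced at diagnosis versus relapse, with a true ratio of 1.0.

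| Advanced at diagnosis | r (months) | m = median from advanced event | Median from first event | Excess | HR, first-event clock |
|---|---|---|---|---|---|
| 70% | 12 | 12.0 | 16.3 | 4.3 | 2.1 |
| 70% | 12 | 24.0 | 29.5 | 5.5 | 1.6 |
| 50% | 12 | 18.0 | 26.8 | 8.8 | 1.8 |
| 50% | 24 | 12.0 | 24.0 | 12.0 | 3.2 |
| 30% | 24 | 12.0 | 31.4 | 19.4 | 3.4 |
| 30% | 24 | 24.0 | 47.2 | 23.2 | 2.2 |

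Medians are from Step 3 (complete follow-up); hazard ratios are from Step 4. On the advanced-event clock, and on the first-event clock with delayed entry at the advanced event, the hazard ratio was 0.98 to 1.01 throughout.

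**Step 5: sensitivity.** The lower end of the excess is about 4 months in every variant. The upper end is about 20 months when the cut-off is applied and about 23 with complete follow-up. With a lognormal time to relapse (log-scale SD 0.5 to 1.0) and the cut-off, the excess is 4.3 to 20.7 months and the hazard ratio 1.5 to 3.7. A fair summary is about 4 to 22 months and about 1.5 to 3.6. With s = 0, S(t) reduces to exp(-a·t) and the excess is 0.

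**The case against.** The strongest reply is that the plan already contains the right definitions. A reader who stops at the unqualified sentence might infer that no OS in the plan measures its stated objective. That is not supported: the next two sentences start OS at unresectable and at metastatic diagnosis, and they match the secondary endpoint.

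A reader might also infer that the Cox models will be run on the first-event clock. The documents do not say so. The prognostic endpoint is worded for the advanced setting, and the one survival model with an explicit origin uses the diagnosis of metastases. Both favour the setting-specific reading. This stands, and it turns a claimed error in the Cox models into an ambiguity. It does not settle the matter. The plan qualifies OS by setting when it means the setting-specific clocks, and the Cox sentence uses the bare term that the plan has defined from the first event.

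Three further points stand in part. Reporting the two settings separately is legitimate and adds no guaranteed time before the advanced stage; the gap is only the missing rule for patients who pass through both. The simulated covariate fixes the guaranteed time directly, so it is close to a worst case. Margins, surgery or neo/adjuvant treatment are affected only as far as they track time to relapse. Finally, the primary objective is descriptive and is not touched.

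What the reply does not remove is the first definition itself: it is a stated outcome, for a cohort selected on a later event, with no correction.

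**Conclusion.** Wrong as written, and it should be fixed before analysis. First-event OS in this cohort includes guaranteed survival time for every patient who enters at relapse. The plan allows for such patients, since both setting-specific definitions provide for entry at diagnosis or at relapse. The OS secondary endpoint does have matching definitions. The open defects are the uncorrected first-event outcome, the unnamed origin in the Cox and TNT-OS analyses, and the missing rule for patients with both settings.

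The size (about 4 to 22 months at the median; a spurious hazard ratio of about 1.5 to 3.6) rests entirely on assumed relapse shares, times to relapse and survival. The hazard ratio applies to the Cox models only if they use the first-event clock. The direction does not depend on the inputs: whenever some patients enter at relapse, first-event OS is longer. Delayed entry recovers a ratio of 1.0 here because the hazard after the advanced event was assumed constant.

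**What to change.** - For the OS endpoint and the Cox models, time OS from the earliest date of unresectable locally advanced or metastatic disease. Count each patient once, and enter the type of first advanced event as a covariate.
- Keep the two setting-specific clocks as secondary or sensitivity analyses.
- State the OS origin used in the TNT-OS correlation.
- Either drop OS from the first tumor event, or analyse it with delayed entry at the advanced event and label it as conditional on progression. Deletion is not essential.

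The cost is SAP wording, a shorter OS figure, and one date. The date of unresectability is not in the plan's list of dates, so it may have to be derived from other fields or abstracted from records. The data dictionary that the plan refers to should be checked for it first.
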